9.9 Definitions for Response Evaluation

9.9.1 Duration of Response

Duration of response—the period measured from the time that measurement criteria are met for complete or partial response (whichever status is recorded first) until the date that recurrent or progressive disease is objectively documented (taking as reference for progressive disease the smallest measurements recorded since treatment started).

9.9.2 Objective Response Rate

The objective response rate is the proportion of all subjects with confirmed PR or CR according to RECIST 1.1, from the start of treatment until disease progression/recurrence (taking as reference for progressive disease the smallest measurements recorded since the start of treatment).

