3 ELIGIBILITY REQUIREMENTS

3.1 Inclusion Criteria

Study entry is open to adults regardless of gender or ethnic background. While there will be every effort to seek out and include men and minorities, the subject population is expected to be no different than that of other advanced solid tumor cancer studies at each participating institution.

Subject must meet all of the following applicable inclusion criteria to participate in this study:

1. Written informed consent and HIPAA authorization for release of personal health information prior to registration. **NOTE:** HIPAA authorization may be included in the informed consent or obtained separately. Patients must be willing and able to provide written informed consent for this trial.
2. Age \geq 18 years at the time of consent.
3. Histologically or cytologically confirmed metastatic uveal melanoma. Staging per AJCC manual edition 8.
4. One or more lesions that could be accurately measured using Response Evaluation Criteria in Solid Tumors (RECIST) 1.1.
5. Eastern Cooperative Oncology Group (ECOG) performance status of 0 to 1 (Appendix 1).
6. Subjects must have archival tissue (metastatic disease preferred) available or undergo a biopsy prior to Cycle 1 Day 1 of treatment. Subjects that do not have archival tissue or cannot undergo a biopsy are not eligible for the study.

7. Demonstrate adequate organ function as defined in the table below. All screening labs to be obtained within 14 days prior to registration.

System	Laboratory Value
Hematological	
Leukocytes	$\geq 2,000 \mu/l$
Absolute Neutrophil Count (ANC)	$\geq 1,500 K/mm^3$
Platelets	$\geq 100,000/ mm^3$
Hemoglobin (Hgb)	$\geq 9 g/dL$
Renal	
Serum Creatinine	$\leq 1.5 \times ULN$
Calculated creatinine clearance ¹	$\geq 40 mL/min$
Hepatic	
Total Bilirubin	$\leq 1.5 \text{ mg/dL}$; (except for subjects with Gilbert Syndrome, who can have total bilirubin $<3.0 \text{ mg/dL}$)
Aspartate aminotransferase (AST)	$\leq 2.5 \times ULN$
Alanine aminotransferase (ALT)	$\leq 2.5 \times ULN$
Alkaline Phosphatase	$\leq 2.5 \times ULN$; ($<5 \times ULN$ if liver metastases present)
Coagulation	
Partial Thromboplastin Time (PTT)	$< 1.5 \times ULN$

¹ Cockcroft-Gault formula will be used to calculate creatinine clearance

8. Prior therapy is allowed but must have been completed 21 days prior to initiation of protocol therapy and all toxicities must be $<$ Grade 2.

9. Palliative radiation must have been completed 2 weeks prior to the initiation of study therapy.

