4: A basic neurologic exam will be performed by the site investigator at screening, Day 1 of each Cycle of treatment and at the D30 safety follow up visit to monitor for neurologic toxicity. The Mini Mental Status Exam (MMSE) will be performed by a member of the research staff at screening and Day 1 of each Cycle of treatment to monitor for cognitive toxicity. The results of the MMSE and neurologic exam will be reviewed by the site investigator who will determine whether dose reduction of study drug(s) is required. This information should be retained.

5: CBC with differential and platelet to include: WBC, ANC, ALC, Hgb, PLT. Comprehensive metabolic profile (CMP) will be done at screening then Day 1 of each Cycle. During Cycle 1, a CMP should be performed at Cycle 1 Day 15. CMP to include glucose, calcium, BUN, creatinine, sodium, potassium, chloride, serum albumin, total bilirubin, alkaline phosphatase, AST, and ALT, ammonia, LDH and uric acid. Coagulation studies (PT/INR and PTT) will be done at screening then at the discretion of the treating investigator during treatment. For women of childbearing potential (WOCBP): urine or serum β hCG if clinically appropriate. If a urine test is done and it is positive or cannot be confirmed as negative, a serum pregnancy test will be required. Testing is required within 72 hours prior to initiation of study treatment. Urinalysis will be performed at screening.

6: Tumor response assessment will consist of evaluation by CT scans of chest and MRI or CT of abdomen and pelvis at screening and every odd numbered cycle starting after screening with CT scan before Cycle 3 (imaging selected for each subject should remain the same throughout the study); tumor imaging to be done at the safety follow up visit is at discretion of site investigator. If tumor assessments are available for subjects who have not yet experienced progressive disease (PD) at the time treatment is discontinued, the follow-up tumor evaluations will be documented in the eCRF until PD or death is confirmed, or until another treatment is initiated. MRI of the brain will be performed per standard of care for those subjects with a history of brain metastasis. A window of - 7 days may be used. CT/MRI images are to be submitted for central analysis. Images will be de-identified prior to sending to a central location. Central analysis to be performed upon receipt of funding.

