9.8 Evaluation of Best Overall Response

NOTE: Revise table if response rate is primary objective of the study, and confirmation of response is required. See Eur J Cancer 45;2009:228-247 for complete details.

Target Lesions	Non-Target Lesions	New Lesions	Overall Response**
CR	CR	No	CR
CR	Non-CR/ Non-PD	No	PR
CR	Not evaluated	No	PR
PR	Non-PD/ or not all evaluated	No	PR
SD	Non-PD or not all evaluated	No	SD
Not all evaluated	Non-PD	No	Non-evaluable
PD	Any	Yes or No	PD
Any	PD*	Yes or No	PD
Any	Any	Yes	PD

In exceptional circumstances, unequivocal progression in non-target lesions may be accepted as disease progression.
All responses will require confirmation with repeat imaging or physical exam at \geq 4 weeks.

Subjects with a global deterioration of health status requiring discontinuation of treatment without objective evidence of disease progression at that time should be classified as having “symptomatic deterioration.” Every effort should be made to document the objective progression even after discontinuation of treatment.

In some circumstances, it may be difficult to distinguish residual disease from normal tissue. When the evaluation of complete response depends on this determination, it is recommended that the residual lesion be investigated (fine needle aspirate/biopsy) to confirm the complete response status.

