12.4.2 Evaluable for Efficacy

Only those patients who have measurable disease present at baseline, have received at least one cycle of therapy, and have had their disease re-evaluated will be considered evaluable for response. These patients will have their response classified according to the definitions stated below. (NOTE: Patients who exhibit objective disease progression prior to the end of Cycle 1 will also be considered evaluable.)

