12.5.2.2 Phase 2 Analysis of Secondary Endpoints

Safety and tolerability by NCI Common Terminology Criteria for Adverse Events (NCI CTCAE) Version 5 on treatment with PAC-1 in combination with entrectinib in subjects with metastatic uveal melanoma.

Proportion of subjects with each grade of adverse events as defined by CTCAE v.5.0 will be computed along with 95% confidence intervals, and reported in a tabular and descriptive manner.

ORR in subjects with metastatic uveal melanoma treated with PAC-1 in combination with entrectinib.

ORR will be estimated according to RECIST 1.1, by dividing the total number of responders (complete plus partial responses) by number of subjects with measurable disease and the exact 95% confidence interval will be computed.

DoR on treatment with PAC-1 in combination with entrectinib in patients with metastatic uveal melanoma.

DoR will be evaluated for subjects who achieve CR or PR using the Kaplan-Meier method. For such subjects, DoR is defined as the number of months from the start date of CR or PR (whichever response status is observed first) and subsequently confirmed, to the first date that recurrent or progression disease (PD) is objectively documented. If a subject dies, irrespective of cause, without documentation of recurrent or PD beforehand, then the subject's date of death will be used to denote the response end date. Subjects who have not progressed will be right-censored at the date of the last disease evaluation. Median DoR will be computed with associated 95% confidence interval, and Kaplan-Meier curves will be plotted.

OS of subjects with metastatic uveal melanoma treated with PAC-1 in combination with entrectinib.

OS will be analyzed using the Kaplan-Meier method, and median OS times will be computed with associated 95% confidence intervals. Subjects who have not died will be right-censored at the date of the last follow-up, and Kaplan-Meier curves will be plotted. Data will be analyzed using the PROC LIFETEST in SAS.

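### ORR is defined on all subjects in 9.9.2 and 12.5.2, but 12.4.2 limits response evaluation to re-evaluated subjects; the plan does not say which applies, and the narrower set can only equal or raise ORR

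*Combined protocol and SAP*

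**What the plan says.** ORR is a named Phase 2 secondary endpoint (2.2.2, 2.5.2). Three places bear on its denominator.

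- Section 9.9.2 gives the definition: "The objective response rate is the proportion of all subjects with confirmed PR or CR according to RECIST 1.1".
- Section 12.5.2.2 gives the calculation, with an exact 95% confidence interval: "by dividing the total number of responders (complete plus partial responses) by number of subjects with measurable disease". Section 12.5.2.1 has the same formula for Phase 1b.
- Section 12.4.2, headed as the efficacy set, admits only subjects who have measurable disease at baseline and who "have received at least one cycle of therapy, and have had their disease re-evaluated will be considered evaluable for response". It makes one exception: "Patients who exhibit objective disease progression prior to the end of Cycle 1 will also be considered evaluable".

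Inclusion criterion 4 in 3.1 requires "One or more lesions that could be accurately measured using Response Evaluation Criteria in Solid Tumors (RECIST) 1.1". Apart from eligibility deviations, the first two denominators are therefore the same people.

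On confirmation, 9.8 states: "All responses will require confirmation with repeat imaging or physical exam", at four weeks or more. Section 9.9.2 also says confirmed, and so does the DoR analysis in 12.5.2.2. The ORR wording in 2.5.2 and the ORR formula in 12.5.2 do not mention it.

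**The concern.** Section 12.4 defines two analysis sets, one for safety and one for efficacy. Faced with an efficacy set that states who is evaluable for response, a programmer could reasonably apply it to ORR. Another could follow 9.9.2 and use everyone. Each could cite the plan, and they would report different rates from the same data.

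The difference has a direction. The first scheduled scan comes before Cycle 3, at about week 8 (two 28-day cycles). Imaging at the safety visit is at the site investigator's discretion, and in long-term follow-up at the physician's (Section 7, footnotes 6 and 13). Subjects who die before a scan, stop in Cycle 1 for toxicity or withdrawal, or come off with symptomatic deterioration and are never rescanned would leave the 12.4.2 denominator. None of them is a responder. The cited trial of selumetinib plus dacarbazine had a PFS of 2.8 months (1.2), so some early loss is plausible.

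With a single arm, the reported ORR will naturally be set beside the 3% and 4% quoted in 1.2. The denominator should not be open to choice once the data are known.

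**Working it through.** **The plan's own figure.** The documents give no target, expected value or power for ORR, so there is no ORR figure to reproduce. The only input taken from the plan's sample size is the Phase 2 total: 32 + 3 for drop-off = 35 (12.3), which agrees with 6 + 29 = 35 (12.3.1). As a check on the 32, an exact binomial test of 0.38 against 0.65 with n = 32 rejects at 18 or more, with one-sided alpha 0.0275 and power 0.888. That is close to the stated 90%. This check does not bear on ORR.

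**Direction.** Let x be the number of responders, n all treated subjects, and k the subjects excluded by 12.4.2. If none of the k is a responder, then

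x/(n − k) ≥ x/n, with ratio n/(n − k).

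The rates are equal only if x = 0 or k = 0. A subject with no re-evaluation cannot be a responder. The inequality could fail only if a subject with less than one cycle of therapy were later scanned and had a confirmed response. That case is assumed not to occur.

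**Size.** The interval is Clopper-Pearson: lower limit Beta(0.025; x, n − x + 1), upper limit Beta(0.975; x + 1, n − x). The responder counts are assumptions. The denominator of 32 takes the plan's 3 drop-offs as unassessed; 30, 28 and 25 are assumed.

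| Denominator | Ratio to 35 | 1 responder | 3 responders (exact 95% CI) |
|---|---|---|---|
| 35 (all) | 1.00 | 2.9% | 8.6% (1.8 to 23.1) |
| 32 | 35/32 = 1.09 | 3.1% | 9.4% (2.0 to 25.0) |
| 30 | 35/30 = 1.17 | 3.3% | 10.0% (2.1 to 26.5) |
| 28 | 35/28 = 1.25 | 3.6% | 10.7% (2.3 to 28.2) |
| 25 | 35/25 = 1.40 | 4.0% | 12.0% (2.5 to 31.2) |

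With 3 responders the shift is 9.4 − 8.6 = 0.8 points at the planned drop-off, and 10.7 − 8.6 = 2.1 points if 7 of 35 are not re-evaluated.

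**Confirmation.** One response more or fewer on 35 subjects moves ORR by 1/35 = 2.9 points, about the size of the 3% in 1.2. It is therefore worth having the endpoint wording and the formula repeat the requirement that 9.8 and 9.9.2 already impose.

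**The case against.** The strongest reply is that both ORR-specific statements, the definition in 9.9.2 and the formula in 12.5.2.2, give the same denominator in practice. Section 12.4.2 is a general dataset definition that the formula does not invoke, so the specific text should govern. That is a sensible reading, but the plan does not state it. Section 12.4.2 is the only efficacy set, is worded exclusively, and speaks of response. The ambiguity stands.

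The reply is right that the bias is bounded. Subjects with objective progression before the end of Cycle 1 stay in the 12.4.2 set, the shift at the planned drop-off is under one point, and the intervals overlap heavily. ORR carries no hypothesis test, threshold or go/no-go role.

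Four stronger readings are tempting, and the documents do not support them.

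- *Three competing denominators.* There are in effect two, because of inclusion criterion 4.
- *Conflicting confirmation rules.* Sections 9.8, 9.9.2 and the DoR analysis all require confirmation; 2.5.2 and the ORR formula are silent. No section says that an unconfirmed response counts. Section 9.8 does keep a template note about revising its table, which is untidy but not a contrary rule.
- *Confirmation by physical exam contradicts footnote 6.* The footnote says "imaging selected for each subject should remain the same throughout the study", which concerns the choice between CT and MRI. Section 9.2 accepts lesions measured with calipers on clinical exam, so confirming those by exam is consistent.
- *A much larger inflation, from adding an unconfirmed response to the smaller denominator.* This needs a response that no section allows to be counted.

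**Conclusion.** The denominator conflict is real. Sections 9.9.2 and 12.5.2 point to all subjects, 12.4.2 points to a re-evaluated subset, and nothing says which governs. The subset can only equal or raise ORR, provided no subject with less than one cycle has a confirmed response. The inflation factor is 1.09 at the plan's own drop-off and 1.25 if 7 of 35 are not re-evaluated, which is an assumption and twice the planned loss or more. Confirmation is a matter of incomplete wording, not contradiction. The effect is confined to how a secondary estimate is reported; the primary endpoint, its conclusion and the sample size are untouched. The correction is still worth making, because the bias runs one way and a choice made after the data are seen would favour the higher figure.

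**What to change.** In 9.9.2, 12.4.2 and 12.5.2, state that the Phase 2 ORR denominator is all treated Phase 2 subjects, that subjects with no post-baseline assessment count as non-responders, and that ORR on the 12.4.2 set is supportive only. Add 'confirmed' to the ORR wording in 2.5.2 and 12.5.2, and say that a response without a confirming assessment is classed as unconfirmed and so does not enter the numerator.

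The cost is wording in both the protocol and the analysis sections, with no added subjects, visits or scans. On treatment, the scans every two cycles can supply confirmation. After treatment stops, imaging is discretionary, so an occasional response may stay unconfirmed. The reported ORR may be slightly lower than under the 12.4.2 set.

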9.9.3 Progression-Free Survival

A measurement from the date of the start of treatment until the criteria for disease progression is met as defined by RECIST 1.1 or death occurs. Subjects who have not progressed will be right-censored at the date of the last disease evaluation.

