2.4 Primary Endpoints

2.4.1 Phase 1b

- The MTD of PAC-1 in combination with entrectinib is the highest tested dose of PAC-1 combined with entrectinib with DLT rate of less than 33% in first cycle of therapy (i.e., ≤ 1 out of 6 subjects with DLT).

2.4.2 Phase 2

- PFS at 3 months; this is defined as proportion of alive subjects with metastatic uveal melanoma at 3 months from treatment initiation with PAC-1 in combination with entrectinib without evidence of radiological disease progression by RECIST 1.1.

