12.3 Sample Size and Accrual

Previous studies in the target population identified PFS at 3 months of 38%.⁶ We hypothesize PFS at 3 months of 65%. Controlling for a probability of Type I error at 0.05 (one-sided), our sample size in Phase 2 is estimated to be 32 to ensure 90% statistical power in successfully detecting an alternative PFS rate at 3 months of 0.65, compared to a null rate of 0.38. With 3 additional patients to account for a 10% drop off rate, sample size for phase 2 study will be 35. Sample size analyses were conducted using the PASS software (NCSS, Kaysville, Utah, USA). With phase 1b study component, the study will need to have 3 subjects from Dose Level 1 of Phase 1b + 6 subjects from Dose Level 2 of Phase 1b (and carried over to Phase 2 study). The total number of subjects for the study is 38.

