12.5.2 Analysis Plans for Secondary Endpoints

12.5.2.1 Phase 1b Analysis of Secondary Endpoints

Safety and tolerability by NCI Common Terminology Criteria for Adverse Events (NCI CTCAE) Version 5 on treatment with PAC-1 in combination with entrectinib in subjects with metastatic uveal melanoma.

Proportion of subjects with each grade of adverse events as defined by CTCAE v.5.0 will be computed along with 95% confidence intervals and reported in a tabular and descriptive manner.

PFS at 3 month in subjects with metastatic uveal melanoma treated with PAC-1 in combination with entrectinib.

PFS will be analyzed using the Kaplan-Meier method, and median PFS will be computed with associated 95% confidence interval. Subjects who have not progressed will be right-censored at the date of the last disease evaluation. Kaplan-Meier curves will be plotted. Data will be analyzed using the PROC LIFETEST in SAS.

ORR in subjects with metastatic uveal melanoma treated with PAC-1 in combination with entrectinib.

ORR will be estimated according to RECIST 1.1, by dividing the total number of responders (complete plus partial responses) by number of subjects with measurable disease and the exact 95% confidence interval will be computed.

DoR on treatment with PAC-1 in combination with entrectinib in subjects with metastatic uveal melanoma.

DoR will be evaluated for subjects who achieve CR or PR using the Kaplan-Meier method. For such patients, DoR is defined as the number of months from the start date of CR or PR (whichever response status is observed first) and subsequently confirmed, to the first date that recurrent or progression disease (PD) is objectively documented. If a subject dies, irrespective of cause, without documentation of recurrent or PD beforehand, then the subject's date of death will be used to denote the response end date. Subjects who have not progressed will be right-censored at the date of the last disease evaluation. Median DoR will be computed with associated 95% confidence interval, and Kaplan-Meier curves will be plotted.

OS of subjects with metastatic uveal melanoma treated with PAC-1 in combination with entrectinib.

OS will be analyzed using the Kaplan-Meier method, and median OS times will be computed with associated 95% confidence intervals. Subjects who have not died will be right-censored at the date of the last follow-up, and Kaplan-Meier curves will be plotted. Data will be analyzed using the PROC LIFETEST in SAS.

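### The PFS censoring sentence leaves out death, so it conflicts with the PFS definition, and the Phase 2 primary analysis section gives no rule that settles it

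*Combined protocol and SAP*

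**What the plan says.** - **9.9.3 (PFS).** PFS runs from the start of treatment to RECIST 1.1 progression or death. The next sentence reads: "Subjects who have not progressed will be right-censored at the date of the last disease evaluation". It does not exclude subjects who have died.
- **2.4.2 (Phase 2 primary endpoint).** For PFS at 3 months, "this is defined as proportion of alive subjects with metastatic uveal melanoma at 3 months from treatment initiation", without radiological progression by RECIST 1.1.
- **12.5.1 (Phase 2 primary analysis).** Three-month PFS is the measure. Median PFS with a 95% confidence interval and Kaplan-Meier curves are planned. No event or censoring rule is given.
- **12.5.2.1 (Phase 1b secondary analyses, PFS).** The text reads: "PFS will be analyzed using the Kaplan-Meier method, and median PFS will be computed with associated 95% confidence interval. Subjects who have not progressed will" and goes on to the same censoring as in 9.9.3. This is the only Kaplan-Meier rule for PFS that is written out in Section 12, and it does not mention death.
- **12.5.2.1 and 12.5.2.2 (duration of response).** The same censoring sentence appears, but directly after a death rule that begins "If a subject dies, irrespective of cause, without documentation of recurrent or PD beforehand" and ends the response at the date of death.
- **12.5.2.2 (Phase 2 secondary analyses).** There is no PFS paragraph.

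**The concern.** Two adjacent sentences in 9.9.3 assign the same record two different outcomes. The definition makes death an event. The censoring sentence covers everyone who has not progressed, which includes a subject who died with no progression on record. The word 'alive' is missing.

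Nothing later settles this for Phase 2. Section 12.5.1 is silent, so a programmer must turn either to 9.9.3, which conflicts with itself, or to the Phase 1b text in 12.5.2.1, which omits death. Elsewhere in 12.5.2 the wording is more careful: duration of response has its own death clause, and overall survival censors only those who have not died.

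An early death is a treatment failure for the primary endpoint. If it were censored, the Kaplan-Meier method would treat it as uninformative loss to follow-up, and the single-arm estimate would look better against the fixed 38% reference.

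**Working it through.** **1. The plan's own figure.** Section 12.3 sets 32 subjects "to ensure 90% statistical power in successfully detecting an alternative PFS rate at 3 months of 0.65", "compared to a null rate of 0.38", with one-sided type I error of 0.05. An exact binomial test with n = 32 needs at least 18 successes. That gives type I error 0.0275 and power 0.888, close to the stated 90%. The normal approximation with continuity correction gives 31. The plan's 32 is therefore reproduced to within rounding and choice of method. It treats each subject as a success or a failure at 3 months, with death a failure.

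**2. Two records under both sentences of 9.9.3.** By Section 7, footnote 6, the first on-study scan comes before Cycle 3 (2 × 28 = Day 56) and the next before Cycle 5 (4 × 28 = Day 112). Only the Day 56 scan falls before 3 months (about Day 91).

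| Record | By the definition | By the censoring sentence |
|---|---|---|
| Stable at Day 56 scan, dies Day 80 | Event, Day 80 | Censored, Day 56 |
| Dies Day 40, no scan after baseline | Event, Day 40 | Censored at the screening scan; adds nothing to the curve |

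**3. Size under the literal reading.** Let S be the true 3-month PFS and d = k/35, where k is the number of deaths by 3 months without documented progression. The documents give no value for k, so 0 to 5 is an assumption.

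- *All k die before the first scan and are censored at baseline.* They leave the risk set, and the estimate is S/(1 − d). For k = 2: 0.38 ÷ (33/35) = 0.403.
- *All k die after the Day 56 scan and are censored there.* No scan falls between Day 56 and 3 months, so they count as progression-free at 3 months, and the estimate is S + d. For k = 2: 0.38 + 2/35 = 0.437.

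| k of 35 | Censored at baseline | Censored at Day 56 |
|---|---|---|
| 0 | 0.380 | 0.380 |
| 1 | 0.391 | 0.409 |
| 2 | 0.403 | 0.437 |
| 3 | 0.416 | 0.466 |
| 4 | 0.429 | 0.494 |
| 5 | 0.443 | 0.523 |

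At a true rate of 0.65, k = 2 gives 0.689 (baseline) to 0.707 (Day 56).

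**4. With deaths counted as events.** The estimate equals the true rate, 0.38 or 0.65, and the figures in step 1 are unchanged.

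**The case against.** The strongest reply is that the plan already counts deaths. The first sentence of 9.9.3 names death as an endpoint, so a subject who has died has reached it and there is nothing left to censor. Section 2.4.2 most naturally makes a death before 3 months a failure. In the duration-of-response text, the same censoring sentence follows a death rule, where it can only mean subjects with neither event. The response definitions in 2.5.2 and 9.9.1 omit death, so 12.5.2 had to add it there; the PFS definition needed no such addition. The repeated PFS sentence also sits under Phase 1b secondary analyses, not the Phase 2 primary analysis.

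Most of this stands. It shows that the likely intent is to count deaths. It does not remove the gap: the censoring sentence still conflicts with the one before it, and 12.5.1 supplies no rule of its own.

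A reader might infer more: that the plan deliberately drops deaths from PFS because it spells them out only for duration of response, or that 2.4.2 puts only living subjects in the denominator. The documents do not support either. Section 9.9.3 does spell out death for PFS, and the denominator reading is the least natural one of an awkward phrase.

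**Conclusion.** This is a wording gap that leaves the handling of deaths open in the Phase 2 primary analysis. It is worth correcting before programming starts. If the sentence is applied literally, deaths by 3 months without documented progression are censored and the 3-month estimate can only go up; median PFS is pushed the same way. With 2 such deaths of 35 and a true rate of 38%, the estimate is about 40% to 44%, depending on when the deaths occur. That range rests on an assumed count and on scans at about Day 56 and Day 112.

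A reader might go further and conclude that 3-month PFS is biased upward, or that the type I error is inflated by a known amount. Neither is established. The bias is zero if there are no such deaths, or if deaths are counted as 9.9.3 defines. The plan states no success cut-off; the 18 of 32 used above is a reconstruction. Any type I error figure would therefore combine an assumed cut-off with an assumed number of deaths.

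**What to change.** In 9.9.3 and 12.5.2.1, replace the censoring sentence with the following, and state it in 12.5.1 for the Phase 2 primary analysis:

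*Death from any cause without prior documented progression is a PFS event on the date of death; subjects alive without documented progression are censored at the last disease evaluation.*

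The cost is wording in three sections. The sample size does not change, and death dates are already collected through the survival follow-up in 5.2 and Section 7. The only consequence for results is that reported PFS may be slightly lower than under the literal rule.
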